1.3 SCHEDULE OF ACTIVITIES (SOA)

	Screening Pre-enrollment	Enrollment/Baseline, Visit 1 Day 0	Procedure, Visit 2 Day 5 (+/- 14 days)	Follow-up, Visit 3 Month 3 (+/- 1 month)	Follow-up, Visit 4 Month 6 (+/- 1 month)	Follow-up, Visit 5 Month 12 (+/- 2 months)	Final Follow-up, Visit 6 Month 24 (+/- 4 months)
Procedures							
Review Inclusion/Exclusion criteria	X						
Informed consent		X					
Demographics		X					
Medical history		X					
Randomization			X*				
Administer study intervention			X				
Slit lamp examination		X		X	X	X	X
Intraocular pressure		X		X	X	X	X
Pachymetry		X		X	X	X	X
Pentacam topography and densitometry		X		X	X	X	X
Endothelial imaging	X	X		X	X	X	X
Clinical photography†		X			X		
BSCVA/ETDRS/MRx		X		X	X	X	X
Baseline form		X					
Follow-up form				X	X	X	X
Final form							X®
Visual function questionnaire		X		X		X	
Cost-effectiveness form							X
Interval History				X	X	X	X
*Randomization performed approximately one week prior to surgery							
†Clinical photography also taken upon adverse event							
®If participant does not complete the study, final form will be filled out at time of withdrawal or loss-to-follow-up							
BSCVA = best spectacle corrected visual acuity, ETDRS = Early Treatment Diabetic Retinopathy Study, MRx = manifest refraction							

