Blindness due to infection may occur in extremely rare cases. There may also be differences in rates of difficulty with donor preparation, increased intra-operative times, graft rejection and graft survival, and donor attachment in DMEK versus UT-DSAEK. Even if there is a total detachment during DMEK, we will continue to move forward with secondary treatment. These risks will be addressed by the enrollment site by making sure all protocols are being followed thoroughly and by following up with participants after surgery.

DETECT

Version 5.0
21 March 2023

There are no known risks directly related to the Endoserter, jones tube, or cannulas. There may be some discomfort during follow-up testing (BSCVA, IOP, slit lamp, Pachymetry, Pentacam, endothelial imaging and OCT testing and photo imaging inside the eye), but this will be kept to a minimum. The participant will be asked to tell the doctor if any of this testing feels painful.

Anesthesiology will be determined as per the participants needs. They will generally be awake with medications given to help them relax and feel comfortable. This is called monitored anesthesia care. Other participants may require general anesthesia care. While this is generally safe, there are small increased risks to the heart and lungs which will be discussed with the anesthesiologist. Both types of anesthesia are routinely used for DMEK and DSAEK surgeries, although generally monitored anesthesia care is the typical route.

The most commonly reported adverse effects of topical ripasudil 0.4% include irritation, blepharitis, honeycomb edema, conjunctival congestion, conjunctival hyperemia, and conjunctival inflammation. Other risks include conjunctival hyperemia, guttata-like bodies with reversible morphologic changes.

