5.5 STRATEGIES FOR RECRUITMENT AND RETENTION

Patients with diseased or damaged endothelium from Fuchs Endothelial Dystrophy or Pseudophakic Bullous Keratopathy will be recruited from the cornea subspecialty clinics of participating institutions for inclusion in the study. For eligible patients the study will be explained in English or the patient's native language using a translator for non-English speakers, in addition to the risks and benefits of participating in the study. The patients will be assured that they can receive all appropriate treatment whether or not they participate in the study. The side effects and drug interaction of all study drugs as well as endothelial keratoplasty are also explained in the consent forms. The study personnel (the study ophthalmologist with the help of the study coordinator) will make sure the patient understands risks, benefits and responsibilities of participating in this trial. Then the study personnel will obtain the patient signature on the consent form.

After the initial screening visit, this trial includes 6 study visits over 24 months. These study visits are:

1. Baseline (pre-operative)
2. Surgery
3. 3 Month Follow-Up (visit window: 2-4 months post-surgery)
4. 6 Month Follow-Up (visit window: 5-7 months post-surgery)
5. 12 Month Follow-Up (visit window: 10-14 months post-surgery)
6. 24 Month Follow-Up (visit window: 20-28 months post-surgery)

For both trials, patients will be randomized by the eye bank one week prior to surgery. At each visit, the study coordinator will work with the patient to schedule their next study visit. The study coordinator will give the patient written documentation of their upcoming visits, and will follow-up with a phone call as their appointments approach. Using this retention strategy, the DETECT-TES had 100% follow-up at 12 months. We are confident that these studies will have high retention as well.

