6 STUDY INTERVENTION

6.1 STUDY INTERVENTION(S) ADMINISTRATION

6.1.1 STUDY INTERVENTION DESCRIPTION

Ultrathin Descemet stripping automated endothelial keratoplasty (UT-DSAEK)

Tissue grafts will be cut to the right thickness using a microkeratome prepared at the eye bank per standard eye bank protocol (about 60-90 microns). The grafts will be punched in the operating room to 7.0- 7.5 mm. A 4 mm corneal incision will be used, with Endoserter as the means of inserting the graft, an FDA approved device for this purpose. Donor tissue or media will be sent for fungal culture by the enrollment site.

Descemet membrane endothelial keratoplasty (DMEK)

Endothelial grafts will be pre-peeled at the eye bank, pre-punched to 7.0 - 7.5 mm and pre-loaded at the eye bank. The endothelium will be stained with trypan blue. The recipient descemets membrane will be stripped to 7.0 - 7.5 mm. A 2.4 mm corneal incision will be used and the graft will be inserted with a modified Jones tube injector, micro Jones tube injector, LEITR glass cannula, micro Stephens glass cannula, or Geuder cannula. The tap technique will be used to position the graft. Donor tissue or media will be sent for fungal culture by the enrollment site.

Descemet Stripping Only (DSO)

The pupil center will be marked in mesopic conditions to guide centration. A 4mm diameter imprint centered on the central mark will be used to guide the descemetorhexis. A reverse sinskey hook will be used to gently initiate a tear in Descemet's membrane and Gorovoy DSO forceps (or similar instrument) will be used to complete the descemetorrhexis

DETECT

Version 5.0
21 March 2023

without disturbing the underlying stroma. The central endothelium will then be gently peeled and removed with forceps.

Ripasudil 0.4%

Ripasudil 0.4% is a selective rho-kinase (ROCK) inhibitor that has been shown to promote endothelial cell proliferation. Patients randomized to receive topical ripasudil will begin medication on post-op day 1. They will take this medication 4 times per day for 3 months.

Placebo

For participants randomized to placebo, they will receive topical placebo in place of topical ripasudil. The placebo will be sodium chloride 0.9%. Those randomized to placebo will receive the topical placebo on the same medication schedule described above for ripasudil.

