6.1.2 DOSING AND ADMINISTRATION

The schedule of medications for the studies are below:

DETECT I Dosing schedule for medications

Medication	Day 1-8	Day 9 – 30	Month 2-3	Month 4	Month 5	Month 6- 12
Ripasudil 0.4% or placebo	4x/day	4x/day	4x/day			
Prednisolone	4x/day	4x/day	4x/day	3x/day	2x/day	1x/day
Ofloxacin	4x/day					

DETECT II Dosing schedule for medications

Medication	Day 1 – 8	Day 9-30	Month 2	Month 3	Month 4	Month 5	Month 6-24
DSO-R Ripasudil 0.4%	4x/day	4x/day	4x/day	4x/day			
Dexamethasone 0.1%	4x/day	4x/day					
(Dexamethasone) placebo			4x/day	4x/day	3x/day	2x/day	1x/day
Ofloxacin	4x/day						
DMEK (Ripasudil) placebo	4x/day	4x/day	4x/day	4x/day			
Dexamethasone 0.1%	4x/day	4x/day	4x/day	4x/day	3x/day	2x/day	1x/day
Ofloxacin	4x/day						

DETECT

Version 5.0
21 March 2023

Participants randomized to receive topical placebo instead of topical ROCK-inhibitors will receive the placebo on the same medication schedule as ripasudil outlined above. If at any time the masked treating physician deems it appropriate to change the patient's treatment, he/she may do so.

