6.2.5 STUDY MEDICATION TRACKING

Once it has been determined that a patient is eligible for the study, their name and mailing address will be entered in REDCap, along with a Baseline Pharmacy Information Form which provides the partner pharmacy with information about allergies and current medications. All study drug tracking will occur within the REDCap database. Randomization into the study will trigger an email notification to the UCSF Study Coordinator, who will communicate with the respective partner pharmacy. The partner pharmacy will be informed of 1) which study arm the patient has been randomized to, and 2) the surgery date. The UCSF Study Coordinator will enter the date and time communication with pharmacy personnel into the REDCap database. All study medication will be dispensed directly to the patient from the corresponding partner pharmacy.

Several days prior to surgery, the pharmacy will prepare the study medication and log into REDCap to enter information about study drug shipment: date and time shipped; lot number; and FedEx tracking info. The site study coordinator or treating physician will contact the patient to ensure receipt of the study drug (Y/N; date received) and review instructions. This will also be logged into the REDCap database. At each study visit, the patient will be asked to bring all bottles of study related medication to review at follow up visits. At the 3- month study visit the study drug bottles will be collected by the study coordinator and any remaining medication will be pulled from the dropper with a syringe to measure the remaining volume. The study coordinator will log the volume in REDCap. Medication adherence questions will be included in the follow-up form at the 3-month study visit.

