In DETECT I, we will examine ECL at 12 months as a key secondary outcome for the UT-DSAEK versus DMEK comparison and will examine BSCVA at 12 months as a key secondary outcome for the ripasudil versus placebo comparison.

Vision-Related Quality of Life. VFQ will be compared between groups using the National Eye Institute Vision-Function Questionnaire 25 (NEI-VFQ-25) at 3 and 12 months controlling for 1-day VFQ. This will be conducted using linear regression with baseline and assignment variables. We estimate the study will be sufficiently large to detect a difference in NEI-VFQ of 4 points, assuming a 2-sided alpha of 5%, 90% power, 110 patients per group, outcome standard deviation of 10.1 and correlation between baseline and follow-up of 0.51 (standard deviation and correlation estimated from NEI-VFQ measurements in the DETECT pilot).⁵²

Endothelial cell morphology. We will use methods similar to the primary analysis for ECL to study the impact of ripasudil on the endothelial cell morphology by comparing the coefficient of variation (CV), variability in hexagonal cell shape (HEX) at the 3-month time point while still on ripasudil as well as at 6, 12 and 24 months after cessation of the study drug.

Pentacam Scheimpflug Tomography. Is a rotating scheimpflug camera, which provides 3 dimensional images of the cornea. In addition to topographic maps with keratometric readings of the anterior and posterior cornea, Pentacam reports on the total corneal power, corneal thickness maps, higher order aberrations and densitometry.

- *Higher order aberrations:* comparing the quantitative measure of irregular astigmatism, expressed in microns as the root mean square (RMS) of the Zernike polynomials across the pupil (approximately central 4 mm of the pupil) controlling for baseline measurements
- *Densitometry:* comparing a measure of corneal reflectance (i.e. scarring) in gray scale units controlling for baseline measurements
- Statistical analysis will be similar to that describe above, linear mixed effects regression using treatment assignment and baseline values as covariates, using the same template as we did for BSCVA.
- For a final supplementary analysis, we will also repeat the BSCVA analyses, but now including Pentacam densitometry at baseline as a predictor. We will report both the regression coefficient for baseline densitometry as a predictor, as well as the coefficient for treatment.

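### The month-3 endothelial morphology comparison is described as on-drug, but about half of the permitted visit window falls after the scheduled course ends, and bottle collection makes no provision for early visits

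*Protocol*

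**What the plan says.** Four provisions of the protocol bear on this point.

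- **Analysis label.** Section 9.4.3, under endothelial cell morphology, plans to study the effect of ripasudil on the coefficient of variation (CV) and hexagonality (HEX) "at the 3-month time point while still on ripasudil as well as at 6, 12 and 24 months after cessation of the study drug". The methods are to resemble those of the primary endothelial cell loss (ECL) analysis.
- **Course.** Section 6.1.1 states: "Patients randomized to receive topical ripasudil will begin medication on post-op day 1" and "They will take this medication 4 times per day for 3 months". Placebo follows the same schedule. In section 6.1.2 the DETECT I dosing row reads "Ripasudil 0.4% or placebo 4x/day 4x/day 4x/day", with nothing entered from month 4.
- **Visit window.** Section 5.5 gives "3 Month Follow-Up (visit window: 2-4 months post-surgery", and the Schedule of Activities in section 1.3 agrees: "Follow-up, Visit 3 Month 3 (+/- 1 month".
- **Bottle collection.** Section 6.2.5 states: "At the 3- month study visit the study drug bottles will be collected by the study coordinator". The remaining drug is then drawn out, measured and logged. The section does not tie collection to completion of the course, and it describes no return or re-supply of drug after an early visit.

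**The concern.** Section 9.4.3 treats month 3 as a measurement under treatment and the later visits as measurements after treatment. That holds only if the month-3 image is taken before the last scheduled dose, and nothing in the protocol requires this. A patient who follows every rule can be imaged well after the course has ended. The label is then wrong for compliant patients and not only for deviators.

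The early side of the window raises a different question. If the bottles are taken and emptied at a visit before month 3, the rest of the course has no stated source of drug. The logged volume would also contain doses that were not yet due.

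At stake are the interpretation of one secondary comparison, the amount of drug delivered to patients seen early, and the meaning of the returned-volume record.

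**Working it through.** The protocol gives no figure to reproduce here, so the check compares dates. Inputs are the start on post-operative day 1 and the 3-month course (6.1.1), the window of 2 to 4 months (1.3, 5.5), and 1 month = 365.25/12 = 30.44 days.

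**Dates**
- Scheduled end of course: 1 + 3 × 30.44 = day 92.3.
- Window opens: 2 × 30.44 = day 60.9.
- Nominal visit: 3 × 30.44 = day 91.3.
- Window closes: 4 × 30.44 = day 121.8.

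**Late visits**
- Longest time off drug at an in-window visit: 121.75 − 92.31 = 29.4 days.
- Share of the window after the course ends: 29.4 / 60.9 = 48%.

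The share of patients affected depends on how visits fall within the window, which the protocol cannot tell us. Assumed patterns give:

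| Assumed spread of Visit 3 dates | Share after last scheduled dose |
|---|---|
| Even over 2–4 months | 48% |
| Normal around month 3, SD 15 days, cut to window | 47% |
| Normal around month 3, SD 10 days | 46% |
| Normal around month 3, SD 7 days | 44% |

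The share is stable because the nominal visit date sits about one day before the course ends. The time off drug is not stable: with tight scheduling, many late visits are off drug by only a few days.

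**Early visits, if collection ends dosing**
- Largest loss, at 2 months: 92.31 − 60.88 = 31.4 days, or 31.4 / 91.3 = 34% of the course.
- Mean loss among early visits, even spread: 31.4 / 2 = 15.7 days, or 17%.
- Mean loss among early visits, normal around month 3: about 0.8 × SD. For SD 7 to 15 days this is about 6 to 12 days, or roughly 6% to 13%.

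**Form of the comparison.** Section 9.4.3 refers back to the ECL model, which in section 9.4.2 compares ripasudil with placebo, adjusting for surgery and the baseline value. The visit window is the same in both arms. No contrast of month 3 against later visits is specified.

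**The case against.** The best defence is that the planned analysis is a randomised comparison at each visit, with one window for both arms. The on-drug phrase is then a loose description and not an estimand. Visits are targeted at month 3, with coordinator scheduling and reminder calls (section 5.5), so most departures should be small. Section 6.1.1 sets a 3-month course without exception, and section 6.2.5 never says that dosing stops at collection. This largely stands. It limits the consequence, but it does not make the description true for late visits or supply the missing instruction for early ones.

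Several stronger readings are tempting, and the documents do not support them.

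- *The drug effect on morphology would show at about half its size.* This needs the effect to vanish at the last dose. The only support is a phrase in the risk section (2.3.1), "guttata-like bodies with reversible morphologic changes", which gives no time course and no link to CV or HEX. The benefit proposed in section 2 is cell proliferation and less apoptosis, which need not reverse in days.
- *The 12-month ECL primary is compromised.* Shortened exposure in some ripasudil patients is possible, but no effect on ECL is shown. Section 9.3 analyses patients as randomised, regardless of adherence.
- *Returned volume will be misread as non-adherence.* Section 6.2.5 only logs the volume and states no rule for converting it. Adherence questions (6.2.5) and patient logs (6.4) are also collected.
- *The course, the window and collection at the visit cannot all hold.* They conflict only for visits before the course ends, and there the fault is silence on what happens next.

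**Conclusion.** The point holds in a limited form. By the protocol's own dates, about the later half of the Visit 3 window lies after the last scheduled dose, by up to about 30 days. The month-3 morphology result therefore cannot be read as an on-drug result. Under the assumed visit patterns, 44% to 48% of patients would be measured after the scheduled end, many by only days if scheduling is tight.

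Read literally, section 6.2.5 also removes up to about a third of the course from a patient seen at 2 months. That rests on the inference that collection ends dosing, and the average loss depends on the unknown spread of visit dates.

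The between-arm comparison is not biased by arm. The fault lies in the label on one secondary analysis and in an unaddressed case in drug handling. It is worth correcting because the correction is cheap.

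**What to change.** 1. Reconcile sections 1.3, 5.5, 6.1.1/6.1.2, 6.2.5 and 9.4.3 on visit timing, course length and bottle collection, including what happens when Visit 3 falls before the course ends. Which clinical provision should prevail is for the investigators. Imaging before the last dose and collection after the course ends fit a single visit on only about one day, so asking for both would mean a second contact.
2. Record the date of last dose at Visit 3.
3. Keep the intention-to-treat month-3 comparison of all eyes. Then either drop the on-drug description in section 9.4.3, or add a supportive analysis that classifies month-3 images by visit date against the scheduled end of the course, identically in both arms. Do not classify by actual last dose, which selects on adherence after randomisation. Visit date is also observed after randomisation, so this analysis should remain supportive.
4. Relate returned volume to days elapsed since the first dose. One line in the statistical analysis plan would do.

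The cost is one date field, one extra supportive analysis, revised wording and possibly tighter scheduling of the month-3 visit, with somewhat more out-of-window visits if the window is narrowed.

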Specific Aim 2: To determine the benefit of adjuvant rho-kinase inhibitors endothelial cell loss in patients who received UT-DSAEK and DMEK

- a. *We hypothesize that endothelial cell loss will be higher after DMEK than UT-DSAEK.*
- b. *We hypothesize that endothelial cell loss will be lessened among those receiving ripasudil, after controlling for the pre-operative ECD in DMEK and UT-DSAEK.*

Secondary Objectives

- Specific Aim 1: To determine whether DMEK has superior post-operative BSCVA at secondary time points
- Specific Aim 2: To assess the effect of surgery type on endothelial cell loss at all time points
- Specific Aim 1: To assess the safety profile of each surgery type
- Specific Aim 2: To determine if rho-kinase inhibitors affect endothelial cell loss in patients undergoing endothelial keratoplasty at secondary time points
- To determine the effect of study interventions on quality of life
- To determine the effect of study interventions on adverse events
- To assess the relative role of light scatter on visual acuity
- To assess the relative role of higher-order aberrations on visual acuity
- To assess the relative role of graft thickness on visual acuity
- To assess the cost-effectiveness of each intervention
- To assess the effect of surgery type on refractive outcomes

DETECT

Version 5.0
21 March 2023**Endpoints:****Primary Endpoints:**

DETECT I

- Best spectacle-corrected visual acuity (BSCVA) at 12 months
- Endothelial cell loss at 12 months

DETECT II

- Best spectacle-corrected visual acuity (BSCVA) at 12 months

Secondary Endpoints:

- Specific Aim 1: BSCVA at 3, 6, and 24 months
- Specific Aim 1: Complications over the course of the entire study period, including re-bubble rate, graft rejection, and primary graft failure
- Specific Aim 2: Endothelial cell density at 3, 6, and 24 months
- National Eye Institute Visual Function Questionnaire (VFQ) post-operatively at 3 months and 12 months as compared to baseline
- Adverse events over entire study period
- Corneal haze and higher-order aberrations as measured by Pentacam at baseline and post-operatively at 3, 6, 12, 24 months
- Graft thickness as measured by optical coherence tomography and pachymetry on donor tissue pre-operatively and post-operatively at 6 and 12 months
- Cost-effectiveness analysis at 24 months
- Manifest refraction at baseline and post-operatively at 3, 6, 12, 24 months

Study Population:

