9.2 SAMPLE SIZE DETERMINATION

DETECT I

We will power the study for each comparison. For both primary analyses, we used a standard sample size formula based on an ANCOVA that conditions on a baseline outcome measure.⁴⁹ Given that endothelial cell density and visual acuity are different, non-correlated outcomes ($R=0.08$ in the DETECT pilot study) with different randomization, each will have its own alpha of 0.05. Specifically, we will be comparing:

- I. With 80 patients per group (160 total), we estimate that we will have at least 90% power to detect a difference in logMAR of 0.11 at 12 months, assuming an outcome SD of 0.2, a 2-sided alpha of 0.05, and 10% loss-to-follow-up. Under the same assumptions but 80% power, the minimum detectable difference in logMAR is 0.09. We assumed a higher SD in the calculation compared with the SD estimated in the DETECT pilot (adj. SD=0.147) to allow for more complex eyes enrolled in the trial.
- II. With 80 patients per group (160 total), we estimate that we will have at least 90% power to detect a 7% difference in ECL between enrollment and 12 months, assuming an outcome SD of 0.134 estimated from the DETECT pilot study, a 2-sided alpha of 0.05, and 10% loss-to-follow-up. If we assume a larger outcome SD for more complex eyes (SD=0.18), we will have at least 90% power to detect a 10% difference in ECL.

DETECT II

With 30 patients per group (60 total), we estimate that we will have at least 90% power to detect a difference in logMAR of 0.13, assuming an outcome SD of 0.147, a 2-sided alpha of 0.05, and 10% loss-to-follow-up. The SD was estimated from the DETECT pilot study and was adjusted for correlation between baseline and 12-month measurements (outcome SD = 0.163, correlation = 0.428, adjusted SD = 0.147). Under the same assumptions but 80% power, the minimum detectable difference is 0.11 logMAR.

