Cost-effectiveness analysis. A supplementary analysis will use individual-level cost outcomes as well as individual-level health outcomes. We propose to report standard cost-effectiveness acceptability curves based on bootstrap resampling at the individual level from both control and intervention subjects (for a statistical, clinical-trial based, cost-effectiveness analysis from a health care system perspective).⁵³ The outcome variable will be cost per line of vision gained.

Treatment allocation survey. We will perform a formal assessment of study participant masking as outlined in SAP 6.4.1

DETECT

Version 5.0
21 March 2023

Adverse Events. All adverse events, including the number of re-bubble procedures, graft failure and graft rejection will be tabulated and reported. Statistical comparisons will be conducted using Fisher's exact test, but with the caution that failure to find evidence of a difference cannot be used to infer a lack of risk difference for rare outcomes such as primary graft failure since the study is not powered to examine these.

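### The cost-effectiveness form is scheduled only at month 24 and has no early-exit version, so participants who leave earlier have no cost form for a listed secondary endpoint

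*Protocol*

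**What the plan says.** The synopsis (1.1) lists "Cost-effectiveness analysis at 24 months" among the secondary endpoints, and the objectives table in section 3 repeats it for each intervention.

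Section 9.4.3 calls the analysis supplementary and takes a health care system perspective. Its inputs are "individual-level cost outcomes as well as individual-level health outcomes", and its output is "standard cost-effectiveness acceptability curves based on bootstrap resampling at the individual level from both control and intervention subjects". It then says: "The outcome variable will be cost per line of vision gained".

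In the Schedule of Activities (1.3), the row "Cost-effectiveness form" has one mark, at Visit 6 (month 24, plus or minus 4 months). The final form is marked in the same column and carries a footnote: "If participant does not complete the study, final form will be filled out at time of withdrawal or loss-to-follow-up". The cost row carries no such footnote. Section 7.2 likewise names only the final status form as brought forward when someone withdraws.

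The health side is collected more often: "BSCVA/ETDRS/MRx" is marked at baseline and at months 3, 6, 12 and 24.

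The missing-outcome rule in 7.3 is triggered by differential loss or by missing primary outcomes. It says nothing about costs.

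**The concern.** Most missing-data questions can be left to an analysis plan. This one differs because it concerns what is collected. An analysis plan can choose how to model missing costs, but it cannot recover a form that was never filled in, and contact with the participant may be gone by then.

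The missing costs may also be the informative ones. The protocol anticipates repeat air injection, re-grafting and, after DSO, a second operation (2.3.1 and 9.4.3). If participants with such courses leave more often, the most expensive cases would be under-represented, possibly to a different degree in each arm. The protocol does not show that this will happen. It is a risk that a small change would reduce.

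**Working it through.** The protocol gives no numerical result for the cost-effectiveness analysis, so there is no figure to reproduce. The check has three parts.

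**1. What exists for a participant who leaves before month 24**

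| Item | Scheduled | Brought forward at early exit? |
|---|---|---|
| Cost-effectiveness form | Month 24 only (1.3) | No provision |
| Final form | Month 24 (1.3) | Yes (1.3 footnote, 7.2) |
| Visual acuity | Baseline, months 3, 6, 12, 24 (1.3) | Known to the last attended visit |
| Interval history, follow-up form | Months 3, 6, 12, 24 (1.3) | Known to the last attended visit |

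The gap is therefore on the cost side. It concerns leaving the study, not stopping study medication: under 7.1, someone who stops the intervention continues with study procedures and would reach the month-24 form.

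**2. How many participants**

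Inputs: 160 participants in DETECT I, 60 in DETECT II, and the planning allowance in 9.2, "a 2-sided alpha of 0.05, and 10% loss-to-follow-up". Number without a cost form = N × loss rate.

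- At 10%: 160 × 0.10 = 16 and 60 × 0.10 = 6, so 22 of 220.
- At an assumed 5%: 220 × 0.05 = 11.
- At an assumed 20%: 220 × 0.20 = 44.

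The 10% is an allowance for the 12-month endpoints. The protocol gives no loss rate for month 24, hence the range.

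**3. What the missing forms could do to the comparison**

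Let a fraction d of an arm leave, and let their true mean cost exceed that of the participants who stay by Δ. The mean among those who stay is then below the arm's true mean by d × Δ. With d = 10% the shortfall is 0.10 × Δ. The observed difference (arm 1 minus arm 0) is off by −(d₁Δ₁ − d₀Δ₀). It cancels if d × Δ is the same in both arms and does not cancel otherwise. The protocol gives no cost figures, so Δ cannot be filled in and neither the size nor the direction of any bias can be stated.

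**The case against.** **Some resource use is recorded elsewhere.** Interval histories and follow-up forms are completed at each follow-up visit, changes of therapy including surgery are recorded (6.5), and adverse events have their own form (8.3.5). The contents of the cost form and the final form are not shown, so one cannot say that early leavers have no cost information at all. This stands, and it limits the point to a missing form.

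**Retention may be better than planned.** Section 5.5 reports 100% follow-up at 12 months in the pilot. This also stands: 10% is not a minimum. A reader might infer that at least a tenth of participants would be dropped, but 9.4.3 states no complete-case rule, and methods for censored or missing costs could be in the SAP, which was not examined here. Nor do the documents support a claim that the cost comparison would have the wrong sign.

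**A form completed at exit gives costs only up to exit.** This is correct. It reduces the gap but does not close it, and a censoring method is still needed.

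**The ratio itself.** A reader might go further and infer that the outcome cannot be computed for eyes that gain no lines. A per-eye ratio is indeed undefined at zero gain and negative when lines are lost. With SD of change = √(SD_b² + SD_o² − 2·r·SD_b·SD_o) and r = 0.428, the pilot's smaller values (0.21, 0.163) give 0.203, and the larger baseline SD with DETECT I's planning SD (0.29, 0.20) gives 0.273. The share of eyes with no gain is Φ(−mean gain/SD): Φ(−0.25/0.203) = 11% to Φ(−0.10/0.273) = 36%, for assumed mean gains of 0.25 and 0.10 logMAR.

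Those figures matter only if the ratio is formed per eye, and the text does not say so. It names costs and health outcomes as separate inputs and plans standard acceptability curves from a two-arm bootstrap. Such a curve is the share of resamples in which λ·ΔE − ΔC > 0, where ΔE and ΔC are the arm differences in mean lines and mean cost and λ is the value of a line. It is defined at zero or negative ΔE and separates cheaper-and-better from dearer-and-worse. In a simulated example with 72 eyes per arm, 36 of 144 eyes had no gain and the curve used all of them.

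**Conclusion.** The point holds as a narrow data-collection gap. The cost form behind a listed 24-month secondary endpoint is scheduled once, and the early-exit provision does not cover it. About 22 of 220 participants would have no cost form if the 10% planning loss applied at 24 months, and 11 to 44 over an assumed 5% to 20%. Bias requires that missing costs differ from observed ones, and differ between arms in extent or size. That is plausible but not shown, and part of the cost may be recoverable from other records.

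The ratio wording is an ambiguity, not a demonstrated error. The importance is minor: the analysis is supplementary, and no primary comparison depends on it.

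**What to change.** In 1.3, attach the early-exit footnote of the final form to the cost-effectiveness form as well, and add the same form in 7.2, so that it is completed at withdrawal or loss to follow-up. State that costs collected this way are censored at the exit date and are not 24-month totals. The form already exists, so the price is a small data-entry burden at exit. The change helps only participants who have not yet left, so it should be made while follow-up is running.

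As an optional clarification, 9.4.3 may state that the cost per line is the arm difference in mean cost divided by the arm difference in mean lines gained, and not a ratio formed for each eye. This is one sentence and changes no data collection.
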